[figure not shown]

Clinical Trial Protocol

Document Number:		c30404410-03
EudraCT No.	2019-005037-37	
BI Trial No.	1407-0041	
Investigational Medicinal Products	Otezla® (Apremilast) film-coated tablets sourced from three ICH regions (EU, US, and Japan)	
Title	Bioequivalence of three different tablet formulations of 30 mg of apremilast (EU-sourced Otezla® vs. US-sourced Otezla® vs. Japan-sourced Otezla®) administered in healthy male and female subjects in the fasted state as well as (for EU-sourced Otezla® vs. US-sourced Otezla®) in the fed state (an open-label, randomised, single-dose, five-period, ten-sequence crossover study)	
Lay Title	A study in healthy people to compare 3 different formulations of apremilast tablets taken with or without food	
Clinical Phase	I	
Clinical Trial Leader	 Phone:  Fax: 	
Principal Investigator	 Phone:  Fax: 	
Status	Final Protocol (Revised Protocol (based on Global Amendment 2))	
Version and Date	Version: 3.0	Date: 05 November 2020
Page 1 of 61		
Proprietary confidential information © 2020 Boehringer Ingelheim International GmbH or one or more of its affiliated companies. All rights reserved. This document may not - in full or in part - be passed on, reproduced, published or otherwise used without prior written permission		

CLINICAL TRIAL PROTOCOL SYNOPSIS

Company name	Boehringer Ingelheim
Protocol date	03 March 2020
Revision date	05 November 2020
BI trial number	1407-0041
Title of trial	Bioequivalence of three different tablet formulations of 30 mg of apremilast (EU-sourced Otezla® vs. US-sourced Otezla® vs. Japan-sourced-Otezla®) administered in healthy male and female subjects in the fasted state as well (for EU-sourced Otezla® vs. US-sourced Otezla®) as in the fed state (an open-label, randomised, single-dose, five-period, ten-sequence crossover study)
Principal Investigator	[REDACTED]
Trial site	[REDACTED]
Clinical phase	I
Trial rationale	The aim of this trial is to establish bioequivalence between EU-, US- and Japan-sourced Otezla® tablet formulations to assure comparability of results from Phase III trials of BI 730357 (new oral agent for treatment of psoriasis [REDACTED] [REDACTED] regardless of whether only the EU-sourced Otezla® or EU- and US-sourced Otezla®/Japan-sourced Otezla® have been used as an active comparator.
Trial objectives	To demonstrate bioequivalence (BE) between EU-sourced Otezla® film-coated tablets, US-sourced Otezla® film-coated tablets and Japan-sourced Otezla® film-coated tablets in the strength of 30 mg. For all tablet formulations their bioequivalence will be tested in the fasted state (BE under fasting conditions) as well as for the EU- and US-formulation in the fed state (BE under fed conditions).
Trial design	Randomised, open-label, single-dose, five-period, ten-sequence crossover design
Trial endpoints	Primary endpoints: AUC _{0-tz} , AUC _{0-∞} , and C _{max} of apremilast in plasma
Number of subjects	
total entered	40 subjects
each treatment	40 subjects
Diagnosis	Not applicable
Main criteria for inclusion	Healthy male/female subjects, age of 18 to 55 years (inclusive), body mass index (BMI) of 18.5 to 29.9 kg/m ² (inclusive)

Proprietary confidential information © 2020 Boehringer Ingelheim International GmbH or one or more of its affiliated companies

Test product (T)	EU-sourced Otezla® (apremilast) film-coated tablet 30 mg (EU-approved)
dose	30 mg apremilast
mode of admin.	Oral administration in the fasted and in the fed state (treatments T_{fasted} and T_{fed}), all with 240 mL of water after an overnight fast of at least 10 h
Reference product (R1)	US-sourced Otezla® (apremilast) film-coated tablet 30 mg (US-licensed)
dose	30 mg apremilast
mode of admin.	Oral administration in the fasted and in the fed state (treatments $R1_{fasted}$ and $R1_{fed}$), all with 240 mL of water after an overnight fast of at least 10 h
Reference product (R2)	Japan-sourced Otezla® (apremilast) film-coated tablet 30 mg (Japan-approved)
dose	30 mg apremilast
mode of admin.	Oral administration in the fasted state (treatment $R2_{fasted}$) with 240 mL of water after an overnight fast of at least 10 h
Duration of treatment	One day (single dose) for each of the five treatments
Statistical methods	
The assessment of bioequivalence will be based upon 2-sided 90% confidence intervals (CIs) for the ratios of the geometric means (test/reference) for the primary endpoints using an acceptance range of 80.00 to 125.00%. This method corresponds to the two one-sided t-tests procedure, each at a 5% significance level. The statistical model will be an analysis of variance (ANOVA) on the logarithmic scale including effects for sequence, subjects nested within sequences, period, treatment and metabolic state (fed or fasted) as well as the treatment-by-metabolic state interaction. CIs will be calculated based on the residual error from the ANOVA and quantiles from the t-distribution.
 
Descriptive statistics will be calculated for all endpoints.

Proprietary confidential information © 2020 Boehringer Ingelheim International GmbH or one or more of its affiliated companies

FLOW CHART

Period	Visit	Day	Planned time (relative to drug administration) [h:min]	Approximate clock time of actual day [h:min]	Event and comment	Safety laboratory ⁸	PK blood (Apremilast)	Vital signs (BP, PR)	Questioning for AEs and concomitant therapy ⁶
SCR	1	-23 to -1			Screening (SCR) ¹	A		x	
1/2/3/4/5 ⁷	2/3/4/5/6 ⁷	-1	-12:00	20:00	Admission to trial site	x ⁵			x
			-11:30	20:30	Snack (voluntary) ³				
		1	-1:00	07:00	Allocation to treatment ² (visit 2 only)	B ²	x ²	x ²	x ²
			-0:30	07:30	Start of high fat, high calorie breakfast prior to treatments T _{fed} and R1 _{fed}				
			0:00	08:00	Drug administration				
			0:30	08:30		x			
			1:00	09:00		x			
			1:30	09:30		x			
			2:00	10:00	240 mL fluid intake	x		x	
			2:30	10:30		x			
			3:00	11:00		x			
			3:30	11:30		x			
			4:00	12:00	240 mL fluid intake	x		x	
			5:00	13:00	Lunch ³	x			
			6:00	14:00		x			
			8:00	16:00		x			
			10:00	18:00	Dinner				
			11:00	19:00		x			
			15:00	23:00		x		x	
		2	24:00	08:00	Breakfast (voluntary) ³ , discharge from trial site	B	x	x	x
			36:00	20:00	Ambulatory visit		x		x
			48:00	08:00	Ambulatory visit		x		x
FU	7	5 to 11			End of trial (EoTrial) examination ⁴	C		x	x

1. Subject must be informed and written informed consent obtained prior to starting any screening procedures. Screening procedures include physical examination, check of vital signs, ECG, safety laboratory (including pregnancy test in women and drug screening), demographics (including determination of body height and weight, smoking status and alcohol history), relevant medical history, concomitant therapy and review of inclusion/exclusion criteria. Pharmacogenetic samples will be collected if needed.
2. The time is approximate; the procedure is to be performed and completed within 3h prior to drug administration.
3. If several actions are indicated at the same time, the intake of meals will be the last action.
4. At the end of trial visit the EoTrial examination includes physical examination, vital signs, ECG, safety laboratory (including pregnancy test in women), recording of AEs and concomitant therapies.
5. Only urine drug screening and alcohol breath test as well as pregnancy test in women will be done at this time.
6. AEs and concomitant therapies will be recorded throughout the trial, but will be specifically asked for at the times indicated in the Flow Chart above.
7. Five identical periods /visits separated by wash-out periods of at least 5 days between the administrations of apremilast.
8. Letter A, B and C define different sets of safety laboratory examinations (see Section [5.2.3](#))

TABLE OF CONTENTS

TITLE PAGE	1
CLINICAL TRIAL PROTOCOL SYNOPSIS	2
FLOW CHART	4
TABLE OF CONTENTS	5
ABBREVIATIONS	9
1. INTRODUCTION.....	12
1.1 MEDICAL BACKGROUND.....	12
1.2 DRUG PROFILE	13
1.2.1 Apremilast	13
1.2.2 Residual Effect Period	14
1.3 RATIONALE FOR PERFORMING THE TRIAL	14
1.4 BENEFIT - RISK ASSESSMENT	14
1.4.1 Procedure-related risks	15
1.4.2 Drug-related risks and safety measures.....	15
2. TRIAL OBJECTIVES AND ENDPOINTS.....	18
2.1 MAIN OBJECTIVES, PRIMARY AND SECONDARY ENDPOINTS	18
2.1.1 Main objectives.....	18
2.1.2 Primary endpoints	18
2.1.3 Secondary endpoint	18
2.2.2.2 Safety and tolerability	19
3. DESCRIPTION OF DESIGN AND TRIAL POPULATION.....	20
3.1 OVERALL TRIAL DESIGN AND PLAN	20
3.2 DISCUSSION OF TRIAL DESIGN, INCLUDING THE CHOICE OF CONTROL GROUP.....	21
3.3 SELECTION OF TRIAL POPULATION	21
3.3.1 Main diagnosis for trial entry	21
3.3.2 Inclusion criteria	21
3.3.3 Exclusion criteria	22
3.3.4 Withdrawal of subjects from treatment or assessments	24
3.3.4.1 Discontinuation of trial treatment	24

FSH	Follicle-stimulating hormone

Proprietary confidential information © 2020 Boehringer Ingelheim International GmbH or one or more of its affiliated companies

FU	Follow-up
GI	gastrointestinal
GCP	Good Clinical Practice
gCV	geometric coefficient of variation
gMean	Geometric mean

IB	Investigator's Brochure
IC ₅₀	50% inhibitory concentration
ICF	Informed consent form
ICH	International Council on Harmonisation
IEC	Independent Ethics Committee

[figure not shown]
IPD	Important protocol deviation
IRB	Institutional Review Board
ISF	Investigator site file
IUD	intrauterine device
IUS	intrauterine hormone-releasing system
λ_z	Terminal rate constant of the analyte in plasma
LC-MS/MS	Liquid chromatography with tandem mass spectrometry
MDA	Methylenedioxymethamphetamine
MDMA	Methylenedioxymethamphetamine
MedDRA	Medical Dictionary for Regulatory Activities
MRT _{po}	Mean residence time of the analyte in the body after oral administration
PDE4	phosphodiesterase 4
PK	Pharmacokinetic(s)
PKS	Pharmacokinetic set
PR	Pulse rate
QT	Time between start of the Q-wave and the end of the T-wave in an electrocardiogram
QTc	QT interval corrected for heart rate using the method of Fridericia (QTcF) or Bazett (QTcB)
R	Reference treatment
REP	Residual effect period

SAE	Serious adverse event
SCR	Screening
SOP	Standard operating procedure
T	Test product or treatment
$t_{1/2}$	Terminal half-life of the analyte in plasma
t_{max}	Time from (last) dosing to the maximum measured concentration of the analyte in plasma
TS	Treated set
t_z	Time of last measurable concentration of the analyte in plasma
TSAP	Trial statistical analysis plan
ULN	Upper limit of normal
V_z	Apparent volume of distribution during the terminal phase after intravascular administration
V_z/F	Apparent volume of distribution during the terminal phase after extravascular administration
WOCBP	Woman of childbearing potential
XTC	Ecstasy

1. INTRODUCTION

1.1 MEDICAL BACKGROUND

BI 730357 is being developed for the treatment of patients with moderate to severe plaque psoriasis and is also under development for the treatment of other disease indications such as psoriatic arthritis, ankylosing spondylitis, and inflammatory bowel disease.

Boehringer Ingelheim (BI) intends to conduct two parallel pivotal Phase III trials designed to demonstrate the superiority of BI 730357 to apremilast (trade name Otezla[®]) as active comparator.

BI currently assumes that each pivotal trial will be conducted globally and plans to use apremilast (Otezla[®]) sourced from three ICH regions (EU, US, and Japan) as the active comparator in the planned Phase III studies of BI 730357.

Apremilast, an inhibitor of phosphodiesterase 4 (PDE4), has been approved in the US since 2014 for the treatment of patients with active psoriatic arthritis, and since 2015 for the treatment of moderate to severe plaque psoriasis. In the EU, apremilast is approved in both indications, psoriasis and psoriatic arthritis. In Japan, apremilast is approved since 2017 for the treatment of plaque psoriasis with inadequate response to topical treatment, and the treatment of psoriatic arthritis. In all three ICH regions, the recommended maintenance dose of apremilast is 30 mg twice daily taken orally (following initial titration starting with 10 mg once daily) [[R20-3168](#), [R20-3173](#), [R20-3422](#)].

Proprietary confidential information © 2020 Boehringer Ingelheim International GmbH or one or more of its affiliated companies

BI intends to use either EU-sourced Otezla® only or EU-sourced Otezla® and US-sourced Otezla® as active comparator in the planned Phase III studies for marketing authorization.

BI conducts this bioequivalence study for the 30 mg strength to demonstrate bioequivalence between EU-approved Otezla®, US-licensed Otezla® and Japan-approved Otezla® tablet formulations in order to allow bridging of the Japan-, US- and EU-sourced Otezla® drug products, i.e. the usage of either EU-approved Otezla® only, or EU-approved and US-licensed Otezla®/Japan-approved Otezla®, in the planned Phase III trials for marketing authorization.

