2. TRIAL OBJECTIVES AND ENDPOINTS

2.1 MAIN OBJECTIVES, PRIMARY AND SECONDARY ENDPOINTS

2.1.1 Main objectives

The main objective of this trial is to demonstrate bioequivalence (BE) between EU-sourced Otezla® film-coated tablets (Test, T), US-sourced Otezla® film-coated tablets (Reference 1, R1) and Japan-sourced Otezla® film-coated tablets (Reference 2, R2) in the strength of 30 mg. All tablet formulations will be tested for bioequivalence in the fasted state (BE under fasting conditions, i.e. T_{fasted} versus $R1_{\text{fasted}}$ and T_{fasted} versus $R2_{\text{fasted}}$) as well as for the EU- and US-formulation in the fed state (BE under fed conditions, i.e. T_{fed} versus $R1_{\text{fed}}$).

[figure not shown]

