7.3.1 Primary endpoint analyses

Primary analyses

The statistical model used for the analysis of the primary endpoints will be an analysis of variance (ANOVA) model on the logarithmic scale. That is, the PK endpoints will be log-transformed (natural logarithm) prior to fitting the ANOVA model. This model will include effects accounting for the following sources of variation: sequence, subjects within

Proprietary confidential information © 2020 Boehringer Ingelheim International GmbH or one or more of its affiliated companies

sequences, period, treatment and metabolic state (fed or fasted) as well as the treatment-by-metabolic state interaction. The effect 'subjects within sequences' will be considered as random, whereas the other effects will be considered as fixed. The model is described by the following equation:

$$Y_{ijklm} = \mu + \zeta_i + s_{im} + \pi_j + \tau_k + \gamma_l + \varphi_{kl} + e_{ijklm}, \text{ where}$$

Y_{ijklm} = logarithm of response measured on subject m in sequence i receiving treatment k under metabolic state l in period j,

μ = the overall mean,

ζ_i = the i^{th} sequence effect, $i = 1, \dots, 10$

s_{im} = the effect associated with the m^{th} subject in the i^{th} sequence,
 $m = 1, 2, \dots, n_i$

π_j = the j^{th} period effect, $j = 1, \dots, 5$

τ_k = the k^{th} treatment effect, $k = 1, 2, 3$

γ_l = the l^{th} metabolic state, $l = 1$ (fed), 2 (fasted)

φ_{kl} = the k^{th} treatment effect ($k=1, 2, 3$) in the the l^{th} metabolic state ($l=1$ (fed), 2 (fasted))

e_{ijklm} = the random error associated with the m^{th} subject in sequence i who received treatment k for metabolic state l in period j.

where $s_{im} \sim N(0, \sigma_B^2)$ i.i.d., $e_{ijklm} \sim N(0, \sigma_W^2)$ i.i.d. and s_{im} , e_{ijklm} are independent random variables.

Point estimates for the ratios of the geometric means ($T_{\text{fed}}/R1_{\text{fed}}$, $T_{\text{fasted}}/R1_{\text{fasted}}$, and $T_{\text{fasted}}/R2_{\text{fasted}}$) for the primary endpoints (see Section 2.1) and their two-sided 90% confidence intervals (CIs) will be provided.

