For each endpoint, the difference between the expected means for $\log(T_{\text{fed}})-\log(R1_{\text{fed}})$, $\log(T_{\text{fasted}})-\log(R1_{\text{fasted}})$ and $\log(T_{\text{fasted}})-\log(R2_{\text{fasted}})$ will be estimated by the difference in the corresponding adjusted means (Least Squares Means). Additionally their two-sided 90% confidence intervals will be calculated based on the residual error from the ANOVA and quantiles from the t-distribution. These quantities will then be back-transformed to the original scale to provide the point estimate and 90% CIs for each endpoint.

Bioequivalence is considered established if the 90% confidence intervals of the geometric means for the primary endpoints are contained in the pre-defined acceptance range, see Section 7.2.

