4. CHANGES IN THE PLANNED ANALYSIS OF THE STUDY

The study was prematurely terminated with only 20 of the 40 planned subjects as the development program of BI 730357 had been terminated in all indications, for the treatment of adult patients with plaque psoriasis, axial spondyloarthritis, and psoriatic arthritis.

Consequently, an abbreviated clinical trial report is planned where data on trial subjects, safety, and PK concentrations will be reported. Only descriptive statistics of PK parameters will be provided; no statistical evaluation of PK parameters will be performed.

In addition, the following change compared to the protocol will be made:

In CTP section 7.3 the following was defined: *Important protocol deviation (IPD) categories will be suggested in the TSAP, IPVs will be identified no later than in the Report Planning Meeting, and the IPV categories will be updated as needed.* Due to SOP changes, the IPD categories are no longer suggested in TSAP, but included in an IPD specification file ([3](#)).

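### Does the protocol promise three-way bioequivalence but leave out the US versus Japan comparison?

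*Protocol*

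**What the plan says.** The title describes the trial as "EU-sourced Otezla® vs. US-sourced Otezla® vs. Japan-sourced Otezla" in the fasted state. Section 1.1 plans apremilast "sourced from three ICH regions (EU, US, and Japan) as the active comparator in the planned Phase III studies", and explains the bridging aim as "bridging of the Japan-, US- and EU-sourced Otezla® drug products, i.e. the usage of either EU-approved Otezla® only, or EU-approved and US-licensed Otezla®/Japan-approved Otezla".

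Section 2.1.1 opens broadly, then narrows at once: "All tablet formulations will be tested for bioequivalence in the fasted state (BE under fasting conditions, i.e" is followed by T_fasted versus R1_fasted and T_fasted versus R2_fasted. EU product is Test; US and Japan products are Reference 1 and Reference 2.

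Sections 7.1 and 7.2 chain the three fasted treatments with the word versus. Section 7.2 then names three ratios: T_fed/R1_fed, T_fasted/R1_fasted and T_fasted/R2_fasted. Section 7.3.1 provides "Point estimates for the ratios of the geometric means" with 90% confidence intervals for the same three, and its success rule reads: "Bioequivalence is considered established if the 90% confidence intervals of the geometric means for the primary endpoints are contained in the pre-defined acceptance range".

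SAP section 4 records termination with 20 of the 40 planned subjects and states: "Only descriptive statistics of PK parameters will be provided; no statistical evaluation of PK parameters will be performed". SAP section 7.4 repeats that the section 7.3.1 evaluation will not be performed.

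**The concern.** The title, section 1.1 and the versus chains in 7.1 and 7.2 can be read as a claim that all three products are mutually equivalent. Two passes against EU product do not prove that. If the true T/R1 and T/R2 both lie within 0.80-1.25, R1/R2 is bounded only by 0.80 × 0.80 = 0.64 and 1.25 × 1.25 = 1.5625.

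Every subject is to receive both R1_fasted and R2_fasted, so the planned model could supply the third ratio at no cost in sample size. If Phase III pooled comparator from all three regions, a reader might take two passes as proof that US and Japan product are interchangeable, although that pair had not been estimated.

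**Working it through.** **1. The plan's own power figure.** Inputs from section 7.7 and Table 3.1: 1: N = 40 (4 per sequence), five periods, gCV 26%, limits ±ln(1.25), 5% per side.

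- Residual df = 200 − 1 − 39 − 4 − 4 = 152.
- σ_w = √ln(1 + 0.26²) = 0.2558; SE = 0.2558 × √(2/40).
- Exact power of the two one-sided tests is 91.0%, 97.5% and 91.7% at ratios 95%, 100% and 105%. Table 7.7: 1 prints the same values.

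**2. Is the third contrast estimable?** The Table 3.1: 1 design matrix gives a variance factor of 0.0500 (= 2/40) for T/R1 fasted, T/R2 fasted, T/R1 fed and R1/R2 fasted. So it is, with the same standard error.

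**3. How far apart can two passes be?** At gCV 26%:

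- 90% CI half-width = t(0.95, 152) × 0.2558 × √(2/40) = 0.0946 on the log scale.
- A ratio passes if |log estimate| ≤ ln(1.25) − 0.0946 = 0.1285, that is between 0.879 and 1.137.
- Opposite extremes give R1/R2 = exp(2 × 0.1285) = 1.293.

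**4. How often would it matter?** Simulation with 4 million draws per scenario, the T_fasted mean shared by both contrasts, and residual variance estimated on 152 df. The true ratios are assumptions. gCV 26%:

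| True T/R1, T/R2 | Both EU ratios pass | All three pass | Of trials passing both, R1/R2 CI not within 80-125% |
|---|---|---|---|
| 1.00, 1.00 | 95.3% | 93.6% | 1.9% |
| 0.95, 1.00 | 89.1% | 83.5% | 6% |
| 0.95, 1.05 | 82.9% | 63.6% | 23% |
| 0.925, 1.075 | 65.4% | 31.6% | 52% |

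The large shares need US and Japan product to deviate from EU product in opposite directions. With both ratios at 0.95 the share is 1.5%. The gCV of 26% belongs to C_max. For AUC_0-tz section 7.7 reports gCVs of about 8% and 20%; at 0.95/1.05 the shares are then about 0% and 12%. Most of these cases are inconclusive intervals: an observed R1/R2 outside 0.80-1.25 occurs in at most 3% of trials passing both.

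**5. Objective against analysis.** This step decides the point.

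| Comparison | Objective (2.1.1) | Estimated (7.2, 7.3.1) |
|---|---|---|
| T_fasted vs R1_fasted | yes | yes |
| T_fasted vs R2_fasted | yes | yes |
| T_fed vs R1_fed | yes | yes |
| R1_fasted vs R2_fasted | no | no |

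The two columns agree row by row. The uses in section 1.1 are EU product alone, or EU product together with US or Japan product; the synopsis rationale and section 1.3 likewise name only uses that include EU product. No visible text sets a US versus Japan objective.

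**6. Can the ratio be called missing?** Protocol headings run from 2.1.3 to 2.2.2.2 and from 7.3.2 to 7.3.4, and the SAP contents list has a blacked-out entry between 7.5.2 and 7.7. A supportive comparison outside the success rule could stand in such a section. Its absence from the visible text does not show that it was unplanned.

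**The case for a change.** The best case for the concern is that the three-way wording is repeated and reaches the statistical section, while the success rule in 7.3.1 does not restate the pairs it covers. The 0.95/1.05 scenario lies within the range that section 7.7 itself uses for planning. One supportive contrast would leave N, alpha and the success rule untouched, and would guard against over-reading two passes.

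Part of this stands. Average bioequivalence is not transitive, the figures are right, and the wording in the title, 7.1 and 7.2 is looser than 2.1.1. That is an editorial remark. The success rule follows directly on the three named ratios and refers back to 7.2, which lists the same three, so its scope is clear. Wording the conclusion as bridging of US and Japan product to EU product would say what 1.1 and 2.1.1 already say. The extra contrast serves no stated objective. Making it a condition of success would lower per-endpoint joint power from 83% to 64% at assumed ratios 0.95/1.05 and gCV 26%, which is a reason to keep it out of the primary rule.

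**Conclusion.** The concern does not hold. The stated fasted objective is a pair of comparisons against EU product, and the planned analysis estimates both and judges them by the stated rule. No number, hypothesis or decision rule in the plan is wrong. A US/Japan ratio would be informative but optional, and it cannot be called missing while parts of both documents are withheld.

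The conclusion rests on section 2.1.1 as the definition of the objective, and on every comparator use described in the protocol including EU product. If a direct US/Japan claim were ever made, it would need its own interval. The visible plan makes no such claim, and with the section 7.3.1 evaluation cancelled, the effect on the abbreviated report is nil.
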